Appendix B: Clinical Efficacy Testing

TABLE OF CONTENTS

STUDY INFORMATION	
SPONSOR	2
CLINICAL CONSULTANT	Error! Bookmark not defined.
MONITOR	
PRINCIPAL CLINICAL INVESTIGATOR	
PURPOSE OF STUDY	
EXPECTED RESULTS	2
STUDY DESIGN	
SUBJECT GROUPS	
DOUBLE BLIND DESIGN	
RANDOMIZATION	
SUBJECTS	4
STUDY PROCEDURE	5
STUDY TEST BATTERY	5
BASELINE VARIABLES	
OUTCOME ASSESSMENT TOOLS	
STUDY PROCEDURE PROTOCOL	
STUDY QUALIFICATION	
STUDY QUALIFICATION EVALUATION	
PRE-PROCEDURE EVALUATION PHASE	
AT-HOME PROCEDURE ADMINISTRATION PHASE	
PROCEDURE ADMINISTRATION	
PROCEDURE ADMINISTRATION PHASE MEASURES	
POST-PROCEDURE ACTIVITIES	
ADVERSE EVENTS	
PRIVACY AND CONFIDENTIALITY	
MONITORING OF THE CLINICAL STUDY	
INFORMED CONSENT	
CASE REPORT FORMS	

APPENDIX D: THL[™] PROPER USE REFERENCE GUIDE APPENDIX K: TINNITUS FUNCTIONAL INDEX (TFI) APPENDIX L: THE TINNITUS FUNUCTION INDEX: DEVELOPMENT OF A NEW CLINICAL MEASURE FOR CHRONIC, INTRUSIVE TINNIUTS APPENDIX M: RESEARCH SUBJECT INFORMATION AND CONSENT FORM APPENDIX N: CASE REPORT FORMS APPENDIX O: RECRUIMENT ADVERTISEMENTS

STUDY INFORMATION

SPONSOR

Erchonia Corporation [name] Contact: [name], President [contact] E-mail: [contact]

REGULATORY AND CLINICAL CONSULTANT

[name] Contact: [name] Principal Consultant [contact] E-mail: [contact]

MONITOR

Erchonia Corporation [name] Contact: [name] [contact] [name] E-mail: [contact]

PRINCIPAL CLINICAL INVESTIGATOR

[name], Au.D [name] Office: [contact]

PURPOSE OF STUDY

The purpose of this clinical study is to determine the effectiveness of the Erchonia® THL[™], manufactured by Erchonia Corporation (the Company), for prescription home use in providing relief of tinnitus symptoms when used by individuals in their own homes.

EXPECTED RESULTS

Following completion of the study procedure administration protocol with the Erchonia® THL [™], it is anticipated that compared with baseline, a significantly greater proportion of subjects in the test group than in the placebo group will show a 13-point or greater reduction in total score on the TFI at study endpoint evaluation relative to baseline.

STUDY DESIGN

This clinical study is a double blind, placebo-controlled, randomized design evaluation of the effect of the Erchonia® THL[™] for prescription home use application in providing temporary relief from the symptoms of tinnitus.

This proposed clinical study design is based on the outcome of Pre-sub Q211668 agreed upon between Erchonia Corporation (Sponsor) and the FDA pertaining to a clinical study evaluating the effectiveness of the Erchonia 405 nm laser for the relief of the symptoms of tinnitus.

SUBJECT GROUPS

Subjects enrolled in the clinical study will not have been enrolled in the Human Factors Validation Testing study.

Each enrolled subject will be randomized to the test procedure group or to the placebo procedure group of the clinical study, as follows:

Test procedure group: Subjects randomized to the test procedure group will self-administer the study procedures with the active (true) Erchonia® THL[™] laser in his or her own home.

Control procedure group: Subjects randomized to the control procedure group will self-administer the study procedures with a 'fake' (placebo) Erchonia® THL[™] laser in his or her own home.

The 'fake' (placebo) laser device will appear to the subject to be an active device but will not produce any therapeutic light output. The placebo laser device is designed to have the same physical appearance as the actual (active) laser device, including the appearance of any visible and invisible light output. Therefore, both the test and control devices emit light when activated that is indistinguishable to the subject. As the laser light does not put out any notable degree of heat or noise, these are also not distinguishing factors for subjects between the active and control devices.

Regardless of whether the subject self-administers the study procedures with the actual or the fake laser device, all subjects will be required to adhere to all phases of the entire protocol design.

DOUBLE BLIND DESIGN

This clinical study is a double-blind design, such that neither the subject nor the investigator is aware of whether the subject has been provided with the active or the placebo Erchonia® THL[™] device. Unblinding will occur after the final data set has been fully analyzed

The blinding procedure is as follows:

- 1) Each device is identified by an arbitrary number (serial number) and will be preassigned by the Sponsor to Group A which corresponds to the actual (test) THL[™] devices or Group B which corresponds to the 'fake' devices. The serial number to device group translation will be maintained by the Sponsor until the final study data set analysis is complete
- 2) Each subject is randomly assigned to Procedure Group A or to Procedure Group B using the computer-generated randomization sequence stored and maintained confidentially at the Sponsor's work site.
- 3) Each subject will be assigned a device serial number by the Sponsor, which translates to Group A or Group B based on the subject's group randomization. The subject and the site personnel will not be aware of any grouping at all. The devices will only be identified by serial number.

4) The fake (placebo) Erchonia® THL[™] is designed to have the same physical appearance as the actual Erchonia® THL[™], including the appearance of any visible and invisible light output. Therefore, both the test and sham devices emit light when activated that is indistinguishable to both the subject and to the investigator. As the laser light does not put out any notable degree of heat or noise, these are not distinguishing factors for subjects between the two groups.

RANDOMIZATION

Subject randomization occurs following attainment of subject consent. Subject allocation to procedure group will be via variable block randomization with varying block sizes of two, four and six used at random to minimize the likelihood of predicting the next procedure group assignment.

Randomization will be attained using computer generation sequence methodology, ensuring that the randomization methodology and the generated allocation sequence is concealed from the subjects.

Concealment will be insured as follows:

- (ii) Each computer-generated randomization sequence is unique and will therefore not be able to be replicated.
- (iii) Randomization will occur to either 'Procedure Group A' or to 'Procedure Group B' rather than to a test or placebo group, and only the Sponsor will know which assignment (A or B) corresponds to the active device and which corresponds to the fake device. Unblinding will not occur until the final study data set analysis is complete.

SUBJECTS

Recruitment

Subjects will be recruited from the test site and online advertisements for individuals who have Tinnitus. Subject recruitment material found in Appendix O.

Compensation

A subject will receive financial compensation of \$150 for his or her participation in this clinical study.

A subject will not be charged for the cost of use of the Erchonia® THL[™] Laser or for the cost of any other evaluations or measurements that occur as part of his or her participation in the study.

Sample Size Determination

The parameters selected for sample size determination are based on the industry-standard reference article: *Tinnitus handicap inventory for evaluating treatment effects: which changes are clinically relevant?* Otolaryngol Head Neck Surg. 2011 Aug;145(2):282-7. Zeman F^1 , Koller *M*, Figueiredo R, Aazevedo A, Rates M, Coelho C, Kleinjung T, de Ridder D, Langguth B, Landgrebe M.

Additional details with respect to the reference values in this article are contained in the Statistical Analysis section below.

STUDY PROCEDURE

STUDY TEST BATTERY

The following are the study assessment tools to be used and the variables to be recorded in this clinical study.

BASELINE VARIABLES

A. Tinnitus Variables

- > Diagnosed etiology of tinnitus, if known. *Responses:* presbyacusis, noise-induced, unknown.
- Number of months/years since tinnitus onset.

B. Medication and Treatment

- > *Prior treatment approaches for tinnitus reduction:* Record all prior treatments, whether conventional or alternative, tried by the subject for tinnitus reduction.
- Concomitant Medication and Therapy Use: Record all over-the-counter and prescription medications currently used for any indication (other than the management of tinnitus symptoms)
- *C. Hearing Aid Use*: yes/no
- D. Subject Demographics: Subject age, gender, and ethnicity.

OUTCOME ASSESSMENT TOOLS

PRIMARY OUTCOME MEASURE ASSESSMENT TOOL:

Tinnitus Functional Index (TFI) (Appendix K)

The Tinnitus Functional Index (TFI) is commonly used in both clinical and research settings for tinnitus measurement due to its responsiveness to treatment-related change, validity for scaling the overall severity of tinnitus, and comprehensive coverage of multiple domains of tinnitus severity (Meikle et al., 2011). The self-report questionnaire, consists of 25 items with a response option on an 11-point Likert scale from 0–10

The calculation of overall TFI score is as follows:

(1) Sum all valid answers (maximum possible score = 250 if the respondent were to rate all 25 TFI items at the maximum value of 10).

(2) Divide (1) by the number of questions for which the sum of the valid answers was based to yield the respondent's mean item score.

(3) Multiply (2) by 10 to attain the respondent's overall TFI score (0-100 range).

Total TFI score can be categorized as Level of Tinnitus Severity as follows:

TFI 0 to 17: Not a problem TFI 18 to 31: Small problem TFI 32 to 53: Moderate problem TFI 54 to 72: Big Problem TFI 73 to 100: Very big problem

DIAGNOSTIC, SECONDARY, and SAFETY OUTCOME ASSESSMENT TOOLS

Audiometric Testing: Degree of Hearing Loss

Audiometric testing will be performed as follows:

- Pure tone air conduction testing for the frequencies of 250 Hz, 500 Hz, 1 kHz, 2 kHz, 4 kHz, 8kHz, 12 kHz, 16 kHz, and 20 kHz
- Pure tone bone conduction testing for the frequencies of 250 Hz, 500 Hz, 1 kHz, 2 kHz, 4 kHz, and 8kHz.

Audiometric testing will be performed using standardized, calibrated equipment that is held constant across all subjects at the test site and administered according to standard industry procedures and protocols.

The audiogram results will be used for two purposes in this study:

(i) Calculation of pure tone average (PTA) as a part of Study Qualification evaluation.

Pure Tone Average (PTA) is calculated as follows: PTA = (500 Hz dB + 1 kHz dB + 2 kHz dB) / 3.

(ii) For tracking of changes in PTA and hearing levels across study duration from 250 Hz through 20 kHz for efficacy and safety evaluation.

Tympanometry

Tympanometry is an objective test of middle-ear function. It is an acoustic evaluation of the condition of the middle ear eardrum (tympanic membrane) and the conduction bones by creating variations of air pressure in the ear canal. Tympanometry, together with audiometry, assists in distinguishing between sensorineural and conductive hearing loss,

The test is performed by inserting the tympanometer probe in the ear canal. The instrument changes the pressure in the ear, generates a pure tone, and measures the eardrum responses to the sound at different pressures. This produces a series of data measuring how admittance varies with pressure, which is plotted as a tympanogram:

Tympanograms are categorized according to the shape of the plot. A normal tympanogram shows normal pressure in the middle ear with normal mobility of the eardrum and ossicles and is labelled Type A. Type B tympanograms indicate (a) fluid in the middle ear, (b) perforation of the tympanic membrane or patent pressure equalization tube, or (c) a tumor in the middle ear. Type C tympanograms are consistent with negative pressure in the middle ear space resulting from compromised eustachian tube function and a retracted tympanic membrane.

A Type A tympanogram accompanied by hearing loss where the air conduction and bone conduction levels on an audiogram are comparable is consistent with a sensorineural hearing loss.

A Type B or Type C tympanogram accompanied by hearing loss where there is a gap / difference between the air conduction and bone conduction thresholds on the audiogram at all or some frequencies is consistent with a conductive or mixed hearing loss.

Otoscopic Exam of the Ears

Otoscopy is a clinical procedure used to examine the structures of the ear, particularly the external auditory canal, tympanic membrane, and middle ear. Otoscopy is performed using a standard otoscope, a tool that shines a beam of light to help visualize and examine the condition of the ear canal and eardrum. The otoscopic exam is performed by gently pulling the auricle upward and backward to move the acoustic meatus in line with the canal.

The appearance of a normal healthy middle ear is as follows:

• Auditory canal: Some hair, often with yellow to brown cerumen.

- Ear drum:
 - Pinkish gray in color; shiny, translucent and in neutral position.
 - Intact; no bulging or retraction.
 - Malleus lies in oblique position behind the upper part of drum.

Observations from the otoscopic examination of the ear will be recorded, taking into consideration the following factors and any other of consideration:

- External auditory canal:
 - Hair (none, some, excessive)
 - Cerumen:
 - color (yellow, brown)
 - amount: minimal, normal ($\leq 50\%$); impacted (> 50%)
 - foreign body (yes/no)
 - Discharge or drainage (yes/no)
- Tympanic membrane
 - Color (pinkish-grey, red, white, yellow)
 - Translucency (transparent, opaque)
 - Position of the drum (retracted, neutral, or bulging)
 - Perforation / scars (yes/no)
 - Cone of light observed (yes/no)
- Position of the malleus handle: normal (behind the upper part of the drum); other

Subject Satisfaction with Study Outcome

The subject is asked to rate how satisfied he or she is with any change in his or her overall tinnitus following completion of the laser administration procedures with the Erchonia® THL[™] by using the 5-point Likert scale presented below to respond to the following question: "Overall, how satisfied or dissatisfied are you with any change in your tinnitus following the study procedures with the study laser device?"

- Very Satisfied
- Somewhat Satisfied
- Neither Satisfied nor Dissatisfied
- Not Very Satisfied
- Not at All Satisfied

BLINDING EFFICACY EVALUATION TOOLS

Subject Perceived Group Allocation and Rationale

The subject records whether he or she believes to have received the study procedures with the true or fake Erchonia® THL[™] and records verbatim his or her reasoning or rationale for this perceived determination.

STUDY PROCEDURE PROTOCOL

STUDY QUALIFICATION

SIGNING OF INFORMED CONSENT FORM

The site investigator will commence by presenting and reviewing the items in the informed consent form with the potential participant and answer any questions he or she may have. To proceed, the individual must willingly sign the informed consent form.

ASSIGNMENT OF SUBJECT IDENTIFICATION NUMBER

The subject is assigned a unique subject identification number based upon his or her order of entry into the study.

Additional information about the informed consent and subject ID number assignment is contained in a later section of the protocol titled, "SAFETY AND CONFIDENTIALITY ISSUES."

SUBJECT RANDOMIZATION TO PROCEDURE GROUP

Following signing of the consent form and prior to study qualification evaluation, a subject is randomly assigned to Procedure Group A or to Procedure Group B, following the methodology outlined above in the STUDY DESIGN section of the protocol.

STUDY QUALIFICATION EVALUATION

A suitably qualified and licensed health professional (study investigator) will perform the study qualification evaluation, at the test site. To be eligible for study participation a subject must satisfy the following qualification criteria.

The study inclusion and exclusion criteria have been separated into two parts: Part 1 and Part 2. This is done to avoid lengthy study tool evaluations (TFI & Audiometric Test) that are involved in Inclusion and Exclusion Part 2, if the subject does not first meet all the Inclusion Part 1 and / or Exclusion Part 1 criteria.

INCLUSION CRITERIA PART 1

To be eligible for study participation, a subject must satisfy each of the following criteria.

- Bilateral tinnitus
- Current diagnosis of subjective tinnitus
- > 18 years of age or older
- Able to read and write English
- Constant tinnitus on-going over at least the past 6 months
- Willing to abstain from other tinnitus-related treatments, except existing hearing aid use, throughout the study duration.

EXCLUSION CRITERIA PART 1

A subject who satisfies any of the following criteria will be excluded from study participation:

- > Tympanosclerosis
- Meniere's disease
- Acoustic neuroma(s)
- Current and consistent use of ototoxic medication(s)
- > Presbycusis
- > Thyroid disease
- Skull fracture
- Traumatic brain injury (TBI)
- Significant depression or other significant mental health condition that in the opinion of the study investigator may interfere with the individual's ability to participate in the study.
- Syphilis
- Retrocochlear tumor(s)
- > Pregnant, possibly pregnant, or breastfeeding.
- > Open wounds (sores, cuts, ulcers, etc.) on or around the ears or neck
- > Cancerous growths or being treated for cancerous growths on or around the ears or neck
- Previous experience self-administering laser therapy
- Difficulty with hand dexterity sufficient to impact ability to administer treatments with the laser such as from severe arthritis in the hands, Multiple Sclerosis, Cerebral Palsy, Parkinson's Disease, Huntington's Disease, etc.

INCLUSION CRITERIA PART 2

A subject that satisfies both the Inclusion Part 1 and Exclusion requirements will proceed to Inclusion Criteria Part 2:

> Tinnitus Functional Index (TFI) total score of 32 to 72, inclusive (Level 3 or 4)

Conduct of the following evaluations:

- Audiometric Testing: calculation of PTA for each ear
- Tympanometry
- Otoscopic Examination of the Ears

•

Based on the outcome of the above evaluations:

- > Pure Tone Audiometry (PTA) is \leq 60 dB (Moderate or less) for each of the right and left ears
- > No hearing loss or sensorineural hearing loss only, bilaterally.

EXCLUSION CRITERIA PART 2

- > Impacted cerumen, foreign bodies, or tubes in one or both ears
- > Perforation of the eardrum in one or both ears
- > Discharge and/or drainage from one or both ears

PRE-PROCEDURE EVALUATION PHASE

The pre-procedure evaluation phase commences the same day following successful study qualification. The pre-procedure evaluation will be performed at the test site and the following will be recorded by the site investigator as outlined in the STUDY TEST BATTERY section above.

BASELINE VARIABLES

- Tinnitus Variables
- Existing hearing aid use
- Medication and Treatment
- Subject Demographics

PRE-PROCEDURE OUTCOME ASSESSMENTS

The Pre-Procedure outcome measures can be taken from the "Study Qualification Evaluation" measures if each are performed on the same day.

- Tinnitus Functional Index (TFI)
- > Audiometric Test: calculation of PTA for each ear
- > Tympanometry
- Otoscopic Examination of the Ears

AT-HOME PROCEDURE ADMINISTRATION PHASE

A fully-qualified enrolled subject will be provided by the study site, a device serial number, which translates to Group A or Group B based on the subject's group randomization. The subject and the site personnel will not be aware of any grouping at all. The devices will only be identified by serial number (see Randomization). The device will include a THL[™] Proper Use Reference Guide **(Appendix D).**

PROCEDURE ADMINISTRATION

- > The procedure administration phase extends over 4 consecutive weeks.
- ➤ The subject self-administers one procedure administration with the Erchonia® THL ™ (A or B) on each consecutive day of the 4-week procedure administration phase for a total of 28 self-administered procedures.
- Each procedure administration lasts 5 minutes each ear, for a total treatment time of 10 minutes.
- > Each procedure is self-administered by the subject in his or her own home.

PROCEDURE ADMINISTRATION PROTOCOL

The subject will need to follow the instructions in the Erchonia THL [™] Proper Use Reference Guide to correctly self-administer a procedure. These instructions read as follows:

1. Turn the THL [™] device on by pressing and holding the "Power Switch" for 3 seconds.

- 2. Ensure the green POWER ON indicator light is lit.
- 3. Put on the laser safety goggles provided.
- 4. Once the safety goggles are on, start the laser treatment by pressing the "START" icon on the treatment screen. Note: The protocol software is factory set and cannot be changed.
- 5. Ensure the laser indicator light is lit.
- 6. Hold the THL [™] laser light diode about 1 inch above your right ear and about 4 inches from your skin.
- 7. In a slow continuous sweeping motion, move the THL [™] down the right side of your neck.
- 8. Once you reach the bottom of your neck, in a slow continuous sweeping motion. move the THL ™ up your neck back to where you started, about 1 inch above your right ear, making sure to keep the laser about 4 inches away from the surface of your skin the whole time. This process is shown in the diagram below.

- 9. Continue this up and down sweeping motion on the right side for the whole 5 minutes of treatment.
- 10. Once the 5 minutes is done, the treatment will automatically stop. The "Time Remaining" display shows 0:00 and the laser lights and the laser indicator light will turn off.
- 11. Next, repeat steps 4 through10 for your left side (left ear and left side of neck) as shown in the diagram below.

12. After you have treated both your right and left ears for a total treatment time of 10 minutes, the treatment session is complete, and you may remove the safety googles.

PROCEDURE ADMINISTRATION PHASE MEASURES

DAILY TREATMENT ADMINISTRATION LOG

The study site will provide the subject data capture forms to record each day when they have administered a treatment with the Erchonia® THL ™ Laser. The subject will provide the study investigator the completed "Treatment administration log" following the 4-week treatment procedure administration phase.

WEEKLY ASSESSMENTS

Once a week, the site staff may call and/or contact the subject by e-mail to check on compliance, to verify that no adverse events had occurred, and to answer any questions the subject may have.

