4 WEEK EVALUATION: TREATMENT END

Following completion of the entire 4 weeks of study procedure administrations with the Erchonia® THL [™], the following will be recorded by the site investigator as outlined in the STUDY TEST BATTERY section above.

- Tinnitus Functional Index (TFI)
- Audiometric Test: Degree of Hearing Loss
- > Tympanometry
- Otoscopic Examination of the Ears
- Subject Satisfaction With Study Outcome
- Subject Perceived Group Allocation and Rationale

POST-PROCEDURE ACTIVITIES

2 Weeks Post-Procedure: STUDY ENDPOINT

Two weeks following the completion of the 4-week treatment administration phase, the following will be recorded by the site investigator) as outlined in the STUDY TEST BATTERY section above. These recordings will form the study endpoint data set from which change from baseline will be evaluated with respect to assessing study outcome.

- Tinnitus Functional Index (TFI)
- Audiometric Test: Degree of Hearing Loss
- > Tympanometry
- Otoscopic Examination of the Ears
- Subject Satisfaction With Study Outcome
- > Subject Perceived Group Allocation and Rationale

ADVERSE EVENTS

The subject will be instructed to notify the PI any time that a potential adverse event has been experienced. It is unlikely and not expected that any adverse events will result from implementation of this clinical study protocol. Prior clinical trials using low level laser light have not typically yielded any adverse events or reactions. However, potential adverse events that may feasibly occur from application of the Erchonia® THL[™] include, but are not necessarily limited to skin irritation, discoloring, rash, indentations, and infection.

PRIVACY AND CONFIDENTIALITY

Records for each subject in this clinical study will be maintained in separate files in a locked filing cabinet at the respective test site. The investigator at the test site will be responsible for ensuring that all records for a subject pertaining to his or her participation in the clinical study are stored in that subject's file at all times other than when information is being recorded on them.

Copies of all of the subject case report forms will be made and supplied to Regulatory Insight, Inc. and Erchonia Corporation. Regulatory Insight, Inc. and Erchonia Corporation will maintain these copies in a separate clinical study file that is kept in a locked filing cabinet at their respective premises. The original records will be maintained at the respective test sites.

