Statistical evaluation of blinding efficacy will be performed as follows:

- (i) The percentage of subjects who correctly perceived their procedure group assignment and the percentage of subjects who did not correctly perceive their procedure group assignment will be calculated.
- (ii) The Fischer's Exact categorical analysis technique for comparison of proportion of successes (accurate procedure group assignment determination) and failures (inaccurate procedure group assignment determination) between subject groups will be performed for each of the subject.
- (iii) **Qualitative analysis confirmation:** Evaluation of the comments provided by the subject in the rationale section to explain the guess at group assignment will be evaluated and interpreted as follows to either support or negate the numerical findings:
 - Positive blinding efficacy will be supported through qualitative assessment of comments provided to support perceived group assignment that pertain to the determination being based on treatment efficacy or lack thereof, e.g.: 'I barely notice my tinnitus anymore, so I believe I got the real treatment' or 'I haven't noticed any change in my tinnitus, so I believe I got the fake treatment.'
 - Blinding will be determined to have failed if comments provided to support perceived group assignment pertain to factors such as sensation/visual clues, such as 'I saw/didn't see a light go on'.

SAFETY ANALYSES

Safety analyses will be based on all subjects who were randomized to the test or to the placebo procedure group. Safety will be assessed by evaluating and comparing frequency and incidence of observed and/or reported adverse events between test and placebo procedure groups. A chisquare test with a continuity correction will be performed to compare the percentage of subjects who had adverse events between test and placebo group subjects.

Additionally, safety will be assessed through tracking of the following across study duration:

- a. changes in audiometric evaluations, including PTAs.
- b. Changes in tympanogram type.
- c. Changes in otoscopic evaluation findings.

INFORMED CONSENT

- Informed consent will be an agreement between the individual investigator and each subject, having the capacity to understand and make an informed decision. Consent will be obtained prior to each potential subject's participation in this clinical study.

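### Laser safety goggles are required at every home session, but goggle use is not described as recorded and eye symptoms are not specifically asked about, so eye safety would rest on general adverse event reports

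*Combined protocol and SAP*

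**What the plan says.** All places below are in the combined protocol and SAP.

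- **Procedure Administration Protocol.** Step 3 is "Put on the laser safety goggles provided", and step 4 starts the laser only after that. Step 12 ends goggle wear once both sides are done: "the treatment session is complete, and you may remove the safety googles".
- **Procedure Administration.** "Each procedure is self-administered by the subject in his or her own home", once a day over four weeks, "for a total of 28 self-administered procedures". No observer is described.
- **Daily Treatment Administration Log.** Subjects receive forms to "record each day when they have administered a treatment". Goggles are not mentioned.
- **Weekly Assessments.** Staff may contact the subject about compliance, adverse events and questions. The contact is optional and no eye question is specified.
- **4 Week Evaluation and 2 Weeks Post-Procedure.** Both lists contain the TFI, audiometry, tympanometry, otoscopy, satisfaction and perceived allocation. Neither contains an adverse event question or an eye item.
- **Adverse Events.** Subjects are told to notify the investigator of any potential event. The examples of feasible events are "skin irritation, discoloring, rash, indentations, and infection", and the list is expressly left open.
- **Compliance Evaluation.** This covers self-reported compliance with treatment administration. Deviations are to be reported and evaluated, but goggles are not named.
- **Safety Analyses.** All observed or reported adverse events are compared by group. Then: "Additionally, safety will be assessed through tracking of the following across study duration", followed by audiometry, tympanogram type and otoscopic findings.
- **Purpose of Study.** The aim is to establish effectiveness for prescription home use, "when used by individuals in their own homes".

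**The concern.** Wearing goggles is a required step in every session, so the plan's own instructions treat the eye as something to protect while a hand-held laser is swept beside the head and neck. The data collection does not follow that through. As described, nothing records whether lay users wore the goggles, and nothing puts a question about the eyes to every subject.

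Two things are at stake. First, an absence of eye complaints in the safety results would be weak evidence, because it would depend mainly on what subjects chose to volunteer. Second, if a complaint did arise, no described record would show whether it followed sessions with or without goggles. Both matter for a device intended for prescription use at home.

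**Working it through.** **Plan's own figure.** The documents give no figure for eye safety, so the only stated number to reproduce is the sample size (Sample Size Determination: 55% against 20%, two-sided alpha 0.05, power 0.80).

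n = [1.960 x sqrt(2 x 0.375 x 0.625) + 0.842 x sqrt(0.55 x 0.45 + 0.20 x 0.80)]² / 0.35²
= (1.342 + 0.537)² / 0.1225 = 28.8, so 29 per group.

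After the dropout adjustment, 29 / 0.917 = 31.62, so 32 per group. Both figures reproduce. The text's one-twentieth dropout differs from the 0.083 used in the formula, but that has no bearing on this point.

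**Unit of exposure.** Goggles go on at step 3 and come off at step 12. For the left side, step 11 repeats only steps 4 to 10. Goggle use is therefore one act per session:
- Active arm: 32 subjects x 28 sessions = 896 planned sessions.
- At 10 minutes each: 896 x 10 / 60 = about 149 hours of planned treatment time.

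**What zero events would show, with every event captured.** The one-sided 95% upper bound on the per-subject risk is 1 - 0.05^(1/n):
- n = 32 enrolled: 1 - 0.05^(1/32) = 0.089, or 8.9%.
- n = 29 completing: 1 - 0.05^(1/29) = 0.098, or 9.8%.

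**Chance of seeing at least one eye event among 32 active subjects, with full capture.** This is 1 - (1 - p)^32. The true risks p are assumptions, since the documents give none:

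| Assumed risk p | Chance of at least one event |
|---|---|
| 1% | 28% |
| 2% | 48% |
| 5% | 81% |
| 10% | 97% |

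Incomplete reporting lowers each of these chances.

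**Routes by which eye information could reach the data, as described:**
1. A subject volunteers a complaint. It would enter the adverse event comparison.
2. A weekly contact elicits one. The contact is optional and its adverse event content is generic.
3. A scheduled visit elicits one. Neither visit list has an item that would do so.
4. The log shows a session without goggles. The log is described as recording treatment days only.

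Routes 1 and 2 exist but are not specific to the eye. Routes 3 and 4 are not described.

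**The case against.** The strongest reply is that adverse event capture is not restricted by body system. Subjects are told to report anything, the list of feasible events is open, staff may ask each week, and every reported event enters the group comparison. That stands. A reader might infer that the trial tracks no eye symptoms, or can say nothing about eye safety. The documents do not support this: a reported eye complaint would be counted, so a clean table would be weak evidence but not empty.

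Other parts of the reply also stand:
- The log and case report forms (Appendix N) and the use guide (Appendix D) are not in the text available. A reader might conclude that the log has no goggle field, but only the protocol's description of it can be judged.
- The adverse event form is also unseen. Nothing in the text prevents an investigator from noting the circumstances of a complaint, so it cannot be said that a link to goggle use could never be made.
- Counting right and left sides separately would give 896 x 2 = 1,792 treatments, but goggles are worn once per session, so 896 is the relevant number.
- One could enlarge the 8.9% bound by assuming that only some events are reported. The documents give no reporting rate, so no such figure is used here.
- The stated purpose is effectiveness, and a separate Human Factors Validation Testing study is mentioned under Subject Groups. Its content is not described and its participants may not enter this trial, so it can be neither credited nor dismissed as evidence on goggle use.

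What the reply does not remove is that the eye is never the subject of a fixed question, that the weekly contact is optional, and that goggle wear is not among the things described as recorded.

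**Conclusion.** The point holds as a modest gap in safety data collection. Goggles are required in all 896 planned active-arm sessions. Goggle use is not described as recorded, and eye symptoms are not specifically asked about. Eye safety in home use would rest on general, largely unsolicited reports from 32 active subjects, with no described record tying a complaint to goggle use.

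The gain from closing the gap is real but bounded. With 32 subjects and full capture, zero events still leaves an upper bound of 8.9%; better capture does not change the sample size. The primary endpoint and its analysis are not affected.

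The conclusion rests on the protocol's description of the log, visits and safety analyses, and would change if Appendix N already contains the missing fields.

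**What to change.** Three additions to existing forms and sections:

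1. **Daily Treatment Administration Log:** one column, *goggles worn for the whole session: yes/no*.
2. **4 Week Evaluation and 2 Weeks Post-Procedure lists:** one fixed yes/no question on eye discomfort or vision change, put to every subject in both groups.
3. **Safety Analyses, tracked items:** one descriptive table giving eye symptoms by group and the number of sessions without goggles.

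If Appendix N already has these fields, it is enough to say so in those three sections. The use instructions stay as they are. The cost is slightly more logging by subjects, one question at each of two existing visits and one table. No extra visits, examinations or staff are needed.
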